- b. Unable to be contacted: 16 intervention participants were randomized but were not able to be contacted by POH to start the intervention and were considered as early withdrawals. Control participants could not be excluded as "early withdrawals" because the next visit would be a month after the baseline. Therefore, researchers modified the protocol and made a phone call to the control participants, right after the randomization, to simulate the call that the intervention participants had by POH to be enrolled in the food and nutrition program. From among control participants called right after randomization in the modified protocol, 2 could not be reached and were considered early withdrawals.

The number of participants with major and minor protocol deviations will be summarized by study arm.

16) Analysis populations – definition of analysis populations, e.g. intention to treat, per protocol, complete case, safety

- a. Intent to treat - The primary analysis will be intent to treat (ITT). The ITT analysis will include all participants in both arms who were randomized, completed all baseline assessments, and who had at least one follow-up visit. (see CONSORT).
- b. Adjusted intention to treat analysis. To adjust for early withdrawals, a propensity score for receiving the intervention will be developed and used to estimate the probability of each participant to receive the intervention. The adjusted ITT analysis will be performed adjusting for the propensity score and for baseline covariates that were different between arms.
- c. Per protocol - The per protocol analysis will include all participants in the ITT sample with baseline and follow-up evaluations and who adhered to the food and nutrition intervention. The minimal adherence will be considered as receiving at least 50% of weeks food and groceries, and at least 1 visit with the dietitian. This definition may be

revised depending on the distribution of adherence in the intervention participants. See appendix 1 for details about the food and nutrition education intervention.

- d. Complete case— We will not conduct complete case analyses as we will attempt to use all available data from all participants.

Section 5: Trial Population

17) Screening Data –

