 1. 16 (15.1%) of randomized intervention and 2 (2.3%) of randomized control participants were unable to be contacted by phone after the baseline evaluations.
 2. 6 (5.7%) participants allocated to the intervention and 2 (2.3%) participants allocated to the control arm were excluded because did not meet eligibility criteria after randomization, and 3 (2.8%) participants in the intervention arm were immediately re-hospitalized.
 3. 1 (0.9%) participant in the intervention arm died after being randomized.
 - ii. Lost to follow up (LTFU) occurred through loss of contact with study participants, moving out of the study area, and death. Intervention participants were also considered LTFU if they withdrew consent. Among

those that were randomized and contacted immediately after randomization (n=79 in intervention arm, and n=82 in control arm):

1. At month 1, 75 (94.9%) of intervention participants and 78 (95.1%) of control participants were retained from month 0.
2. At 5 months of follow-up, 60 (75.9%) of intervention participants and 59 (71.9%) of control participants were retained from month 0.

b. Timing of withdrawal/LTFU data

- i. Intervention participants left the study prior to their first encounter with Project Open Hand were considered withdrawn, otherwise they were considered LTFU.
- ii. Control participants that left the study prior the first call from UCSF staff were considered withdrawn, otherwise they were considered LTFU.
- iii. Participants that were excluded immediately after randomization were also considered early withdrawals.

c. Reasons and details of how withdrawal/LTFU data will be presented

- i. Withdrawal and LTFU data are presented in the CONSORT diagram, stratified by study arm and visit. These data are included to establish lack of bias in screening and retention between the two arms. (See appendix 2)

21) Baseline patient characteristics

We will evaluate several socio-demographic and clinical characteristics at baseline by which we will describe our study sample. These are outlined in Table 1 below and a shell table is provided in the appendix. We will stratify these characteristics by intervention and control arms and report median and the inter-quartile range for continuous variables with skewed data and mean and SD for continuous variables with normal distribution. Categorical variables will be presented as numbers and percentages. No significance testing will be conducted or reported at baseline per CONSORT guidelines.

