- a. **Preliminary/Descriptive analyses.** Frequency tables for all variables and measures of central tendency and variability for continuous variables will characterize the sample and be stratified by randomization arm to check for non-equivalence. If the two arms differ at baseline on any covariates, propensity scores approach will be used to obtain the desired marginal effect estimates under the counterfactual assumption of balanced arm.

25) Analysis methods to be used and how the treatment effects will be presented:

- a. Aim 1, Hypothesis 1. The intervention will lead to improved heart failure quality-of-life (primary outcome) and reduced acute care utilization (secondary outcomes) in the intervention arm compared to the control arm. Intent-to-treat analyses will assess whether the intervention will result in improved changes in primary and secondary outcomes with mixed effects models. These mixed models are equivalent to repeated measures models. Study arm (intervention or control), visits (baseline, month 1 and month 5), and the interactions between arms and visits will be the fixed effects and individuals will be considered as random effects.

Alternative analyses will be done using analysis of covariance in which the 5 month (and 1 month) outcome measures will be regressed on the corresponding baseline outcome measures and study arm. Analysis of covariance allows relaxing the assumption that the

baseline and follow-up measures have a 1:1 relationship and testing the assumption that the relationship between the baseline and follow-up measures are the same.

Additional analyses will be done to check robustness if the two arms differ at baseline by controlling for the propensity score or the covariates that were important in the propensity score.

For primary and secondary outcomes, Box-Cox transformations will be used to correct for skewness if needed.

To compare the probabilities of hospitalization and emergency room visits by study arm, a log-rank test will be performed, and visualized using Kaplan-Meier curves.

- b. Aim 2, Hypothesis, The intervention will improve food security, reduce healthcare utilization, and improve dietary behavior, that in turn will improve mental health (depressive symptoms), and medication adherence. Analysis for intermediate outcomes will be performed using mixed effects models, as described in Aim 1.
- c. Any planned sensitivity analyses for each outcome, where applicable: Not applicable.

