Any planned subgroup analyses for each outcome including how subgroups are defined: Additional models and statistical interactions (i.e., product terms) will be performed to identify characteristics of individuals who most benefitted from the intervention, such as biological sex, and food insecurity.

24) Missing data

- a. The study team employed several strategies to account for and address missing data during the CaRDS trial period. To prevent or reduce missing data, data collection was computerized, and the questions were obtained through a trained interviewer. The analyst will examine patterns of non-response and inspect distributions of mediating and outcome variables to identify outlying or unusual values and assess distributional characteristics. Missing data will be categorized into: 1) missed individual questions, 2) missing forms, and 3) missed visits.
- b. Missed individual questions: Multiple imputation will be used to address incomplete data arising from missing forms. The assumption will be that incomplete data arise from a conditionally missing-at random mechanism (MAR). Auxiliary variables will be included to help meet the MAR assumption and sensitivity analyses will be conducted with weighted multiple imputation to assess the MAR assumption. Information on percent of questions missing and imputed will be reported for each variable as appropriate in study manuscripts. Missing items from a scale will be imputing using the other items in the scale.
- c. Missed visits: When a participant missed a visit, either home or clinic or both, this was noted in the study register.

25) Additional analyses – None

26) Harms

i. Data safety:

The study team took several proactive strategies to insure the highest levels of data safety. First, data were collected on password protected tablets or laptops. Data were collected using REDCap and stored on a secure UCSF server. The data was stored in a separate folder than other study materials, and only members of the data team had access to this data. Lastly, any individual who requests study data was required to sign a data agreement which included not sharing the data as well as recommendations for data safety. No identifiers have or will be shared with external investigators.

ii. Details on how adverse events are coded or categorized:

Deaths were reported to UCSF by email within 24 hours after the PIs learned of the occurrence. Other adverse events were not reported.

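### The primary set labelled intent to treat requires a follow-up visit, so early withdrawals (27/106 vs 4/86) fall outside it and no stated analysis clearly brings them back

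*Combined protocol and SAP*

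**What the plan says.** **Set.** Section 4, item 16a names the primary analysis ITT and admits participants "who were randomized, completed all baseline assessments, and who had at least one follow-up visit". Section 6, item 25a uses it for both outcome tiers: "Intent-to-treat analyses will assess whether the intervention will result in improved changes in primary and secondary outcomes with mixed effects models".

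**Early withdrawal.** Section 5, item 20b defines it by arm: "Intervention participants left the study prior to their first encounter with Project Open Hand were considered withdrawn" and "Control participants that left the study prior the first call from UCSF staff were considered withdrawn". Item 20b also counts exclusions made immediately after randomisation, without reference to arm. Section 4, item 15 explains that controls at first had no comparable contact point, so a phone call was added "to simulate the call that the intervention participants had by POH to be enrolled in the food and nutrition program". The number of controls called is not given.

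**Retention.** Item 20 starts from 79 and 82, after early withdrawals have been removed. Item 20c says of the withdrawal and follow-up data: "These data are included to establish lack of bias in screening and retention between the two arms".

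**Remedies offered.** Item 16b adjusts for early withdrawal with a propensity score for receiving the intervention. Item 16d intends to use whatever data exist from every participant. Section 6, item 24b says "Multiple imputation will be used to address incomplete data arising from missing forms" and adds that "sensitivity analyses will be conducted with weighted multiple imputation to assess the MAR assumption". Item 24c says only that missed visits were logged.

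**The concern.** A set that depends on what happens after randomisation no longer compares the groups as randomised. Here the excluded share is about 21 percentage points larger in the intervention arm. A patient whom the food provider could not reach is a non-starter, and ITT is meant to keep non-starters in.

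The admission and emergency outcomes make this more pressing. Section 3, item 11 says medical records were collected in both arms from 3 months before to 9 months after baseline. Counting an admission to the trial hospital (ZSFG) therefore needs no study visit. Yet under 16a and 25a a patient with no visit drops out of those outcomes, including three intervention patients whose reason for withdrawal was re-hospitalisation.

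Readers who see the ITT label, with near-equal retention percentages beside it, would assume a protection that this set does not give.

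**Working it through.** **Inputs.** Randomised 106 and 86; early withdrawals 27 and 4 (item 19). Reasons (item 20): contact failure 16 vs 2, ineligibility 6 vs 2, immediate re-hospitalisation 3 vs none listed, death 1 vs none listed. Retained 75 vs 78 at month 1 and 60 vs 59 at month 5 (item 20). SD 20 and a 10-point target (item 7).

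**1. Retention: the plan's figures, then all randomised**

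| | Plan's denominators (79, 82) | All randomised (106, 86) |
|---|---|---|
| Month 1 | 75/79 = 94.9% vs 78/82 = 95.1% | 75/106 = 70.8% vs 78/86 = 90.7% (p = 0.0006) |
| Month 5 | 60/79 = 75.9% vs 59/82 = 71.95% (quoted as 71.9%) | 60/106 = 56.6% vs 59/86 = 68.6% (p = 0.10) |

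The plan's figures reproduce. At month 5 the order of the arms reverses when the denominator changes.

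**2. Imbalance in early withdrawal (Fisher exact)**
- All: 27/106 = 25.5% vs 4/86 = 4.7%, difference 20.8 points, p = 0.00006.
- Contact failure, the part whose trigger differs by arm: 16/106 = 15.1% vs 2/86 = 2.3%, p = 0.002.
- Ineligibility, one reason listed in both arms: 6/106 vs 2/86, p = 0.30.
- Without the ineligible: (27 − 6)/(106 − 6) = 21/100 vs (4 − 2)/(86 − 2) = 2/84, p = 0.00009.

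**3. Size of the 16a set.** It holds 75 to 79 of 106 (70.8% to 74.5%) and 78 to 82 of 86 (90.7% to 95.3%), depending on whether patients who missed month 1 had a later visit. The text gives no exact number.

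**4. KCCQ.** Assume excluded patients would have changed D points less than the others in their arm; D may have either sign and is not given in the documents. The arm difference then shifts by D × (missing share, intervention − missing share, control).
- Only early withdrawals differ, later losses unrelated to outcome: 27/106 − 4/86 = 0.208, so 0.21D.
- Everyone missing at month 5 differs: (106 − 60)/106 − (86 − 59)/86 = 46/106 − 27/86 = 0.120, so 0.12D.

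With 60 vs 59 patients, SE = 20 × √(1/60 + 1/59) = 3.67. With no true effect, the two-sided false-positive rate is P(|Z + shift/SE| > 1.96).

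| D | Shift at 0.12D | False-positive rate | Shift at 0.21D | False-positive rate |
|---|---|---|---|---|
| 5 | 0.6 | 5.3% | 1.0 | 5.9% |
| 10 | 1.2 | 6.2% | 2.1 | 8.8% |
| 15 | 1.8 | 7.8% | 3.1 | 13.6% |

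A negative D reverses the sign of the shift. These are two illustrations, not bounds: if only the intervention withdrawals differed, the factor would be 27/106 = 0.255. Under the 0.208 factor, a shift of the full 10-point target needs D = 10/0.208 = 48.

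**5. Readmission, intervention arm.** Let r be the risk among all 106 (assumption) and x the number readmitted among the 27. Excluding them gives (106r − x)/79, which is below r only if x > 27r: 2.7, 5.4 or 8.1 at r = 10%, 20% or 30%. With only the three known cases (x = 3), 10% becomes 9.6%, 20% becomes 23.0% and 30% becomes 36.5%. With x = 9, 20% becomes 15.4%. The exclusion can push the estimate either way.

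**The case against.** **Disclosure.** The set definition, counts and reasons are all stated, and the reason percentages use 106 and 86. Modified ITT sets are common, and this is described as a pilot. That rules out any suggestion of concealment. It does not make the set ITT, and item 8 specifies superiority testing.

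**Arm-specific removal.** A reader might infer that all 31 early withdrawals were removed under rules that differ by arm. The documents do not support that. Only contact failure has different triggers; ineligibility is listed for both arms, and item 20a gives death as a general reason. Item 16a has the same wording for both arms and does not name early withdrawals: their absence follows from the visit condition and from item 20.

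**Items 16b and 16d.** A reader might infer that the plan ignores early withdrawal. It does not: 16b is aimed at it, and adjusting for predictors of withdrawal can reduce selection bias without supplying missing outcomes. But 16b models receipt of the intervention rather than remaining in the study, and states no analysis set. Item 16d conflicts with 16a and names no method. The log-rank analysis in 25a names no set either.

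**Mixed model and imputation.** A mixed model accommodates a missed visit only for patients admitted to the set. Item 24a separates missed questions, missing forms and missed visits; 24b covers the first two.

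**Unseen material.** The CONSORT diagram is not shown and may give the numbers analysed. The text does not say whether record access covers early withdrawals. Both caveats stand.

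**Conclusion.** The concern holds. The primary set is a modified ITT set under an ITT label, early withdrawal is strongly unbalanced (25.5% vs 4.7%), and no stated analysis clearly restores those patients. The label, the missed-visit method and the set for record-based outcomes should be corrected before analysis.

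For KCCQ the effect is modest under the assumptions shown: 1.2 to 2.1 points at D = 10, with a false-positive rate of 6.2% to 8.8% instead of 5%. D itself is an assumption.

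Two stronger readings are not supported. One is that the exclusions favour the intervention: the outcomes of most excluded patients are unknown, so the net direction is not established for readmission or KCCQ. The other is that events were removed from one arm only: re-hospitalisation and death are listed for intervention alone, but outcomes of the four excluded controls are not given.

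Two count differences are reporting points only. Item 6 gives 3 control withdrawals and item 19 gives 4, but item 6 may describe an earlier time. The itemised intervention reasons sum to 16 + 6 + 3 + 1 = 26, not 27, and the CONSORT diagram may supply the other. The imbalance remains with 26 (p = 0.0001).

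**What to change.** 1. Analyse ZSFG-record admissions and emergency visits, including the log-rank comparison, in all 192 randomised patients as allocated, whether or not a study visit took place. Censor at death or withdrawal of consent to record access, and state whether record access covers early withdrawals.
2. Rename the 16a set modified ITT, keep it as a sensitivity analysis, and reconcile it with 16d.
3. For KCCQ, analyse all randomised patients with a baseline score. Extend the 24b imputation and its MAR sensitivity analysis to missed visits, by arm, with a delta range over both signs and deaths handled separately. State the analysis set for 16b.
4. Report retention also from 106 and 86, and reconcile the two count differences.

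**Cost.** SAP wording, possible record abstraction for about 31 patients (27 + 4), and a few more model runs. Estimates may become less favourable or less precise. The main gain is in the record-based outcomes. For KCCQ it is a correct label and a stated range, because patients with only a baseline score add little without the imputation step.

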The primary outcomes were established in the protocol, and thus no adjustments will be made for multiplicity.

14) Confidence intervals

95% confidence intervals will be reported alongside exact p-values.

15) Adherence and protocol deviations

- a. Definition of exposure to the intervention and how this is assessed including extent of exposure:
 - i. Receipt of medically tailored food support AND
 - ii. Receipt of nutrition counseling and/or education
- b. Description of how adherence to the intervention will be presented.

Adherence to the intervention will be presented through a narrative summarizing the following points:

- i. % of weeks received any food support (out of weeks scheduled to receive food support)
- ii. % of food received (out of total food entitlement) (POH data)
- iii. % of food consumed (out of food received) (survey data)

iv. % of counseling or education sessions received (out of planned sessions) The cut-off points to decide if the patient is adherent to the intervention will be defined during the analysis, based on the participant's exposure to the intervention.

Definition of protocol deviations for the trial. The following protocol deviation occurred during the study and corrective actions were developed:

- a. Minor protocol deviation: Participants for study visits were seen outside of the initial protocol specified visit window (+/- 1 month). All efforts were made to reach the participants on time, but the participants were not available or were not able to be located within the window and therefore they were seen outside of the visit window. As a result, the standard operating procedure (SOP) was updated that addresses follow up and retention of participants. The SOP outlines that the research assistants will make calls and conduct home visits in case a participant misses his or her appointment date to ensure that the participants are seen with the appointment window period.

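### The per-protocol adherence cut-off can be set or changed during the analysis, with no lock and no stated control comparator, so this non-primary result is open to cut-off selection and selection bias

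*Combined protocol and SAP*

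**What the plan says.** Two items in Section 4 of the combined protocol and SAP bear on who counts as adherent.

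- **Item 16c (per protocol)** draws the set from ITT participants with baseline and follow-up evaluations "who adhered to the food and nutrition intervention". It sets a minimum of "at least 50% of weeks food and groceries, and at least 1 visit with the dietitian", then says this may be "revised depending on the distribution of adherence in the intervention participants".
- **Item 15b (presentation of adherence)** lists four measures: weeks with any food, share of food received, share of food consumed, and share of sessions received. It gives no threshold. It says the "cut-off points to decide if the patient is adherent to the intervention will be defined during the analysis". The only ground it names for that choice is how much of the programme each person received.

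Item 16a makes ITT the primary analysis. Item 16b attaches the propensity score to the adjusted ITT analysis, not to the per-protocol one. Item 10 starts the final analyses after field and medical-record data collection is complete. No item freezes the adherence definition, keeps the person choosing it blind to outcomes, or says that the default and any revised rule will both be reported. Item 16c does not say which controls enter.

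**The concern.** There are two separate weaknesses.

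**The rule is not settled before outcomes exist.** An analyst following item 15b and one following item 16c could build different per-protocol sets from the same data. Nothing stops someone from seeing the treatment difference under several cut-offs before settling on one, and a reader of the results could not rule that out.

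**The set is formed on something measured after randomisation, in one arm.** Controls had usual care during the study period and the meal programme only afterwards (item 5), so they had nothing to adhere to. The background text says that medication access and life chaos contribute to readmission in this population. The same factors could plausibly affect whether a person accepts deliveries and dietitian visits. If so, adherers would have done better than average without the food, and a comparison with unselected controls would favour the intervention.

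At stake is the credibility of the per-protocol estimate, which readers may take as the effect in people who actually received the programme.

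**Working it through.** **Step 1. The two items side by side.**

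| | Item 15b | Item 16c |
|---|---|---|
| Measures | four | two (weeks of food, dietitian visits) |
| Threshold | none | 50% of weeks and 1 visit |
| When settled | during the analysis | default now, revisable later |
| Stated basis | exposure | adherence distribution |
| Controls | not mentioned | not mentioned |

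The conflict is between a revisable default and no default. Neither basis is an outcome, but outcomes will be in hand when either choice is made.

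**Step 2. The plan's own figure (item 7).** With SD 20, difference 10, two-sided 0.05 and 80% power: n = 2 × (1.96 + 0.84)² × 20² / 10² = 62.8, so 63 per arm. Then 63 / 0.80 = 78.75, so 79 per arm and 158 in total. Both stated figures reproduce, so no arithmetic error is involved. The plan gives no power for the per-protocol set.

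**Step 3. Inputs for sizing.** From the documents: 60 intervention and 59 control participants retained at month 5 (item 20), SD 20 and a 10-point difference (item 7). Assumed, because the documents do not give them: the adherence distribution, the correlation ρ between adherence and change in the quality-of-life score (0 to 0.3), the candidate cut-offs, and comparison with all retained controls. The true effect is set to zero.

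**Step 4. Selection bias in points.** If the most adherent share p is kept, bias = ρ × 20 × φ(z)/p, where z is the normal quantile at 1 − p. For p = 0.75, φ(z)/p = 0.318/0.75 = 0.424. For p = 0.50, it is 0.399/0.50 = 0.798.

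| Share kept | ρ = 0.1 | ρ = 0.2 | ρ = 0.3 |
|---|---|---|---|
| 90% | 0.4 | 0.8 | 1.2 |
| 75% | 0.8 | 1.7 | 2.5 |
| 50% | 1.6 | 3.2 | 4.8 |

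The planned difference is 10 points.

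**Step 5. False positives in simulated null trials.** Each trial uses a two-sided t-test of adherers against all 59 controls. Model A has adherence spread evenly and a cut-off on weeks only, with candidates 25, 50, 75 and 90% (8,000 trials per row). Model B applies the two-part rule (about 63% meet the default), with 15 candidates: five week thresholds crossed with three visit counts (5,000 trials per row). The selected columns take the smallest p-value among the candidates, the worst case for steering.

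| ρ | A: fixed 50% | A: best of 4 | B: fixed default | B: best of 15 |
|---|---|---|---|---|
| 0 | 5.2% | 12.9% | 5.0% | 16.4% |
| 0.1 | 6.5% | 16.1% | 6.1% | 19.2% |
| 0.2 | 11.5% | 25.2% | 8.5% | 27.2% |
| 0.3 | 18.9% | 38.2% | 14.0% | 40.3% |

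Another run of model A gave 4.8% and 12.0% at ρ = 0, and 10.6% and 22.5% at ρ = 0.2. With adherence skewed high (Beta(4, 1.5), about 88% meeting 50%), the fixed rule gives 5.3% at ρ = 0.1 and 6.0% at ρ = 0.2, while picking among four cut-offs still gives about 12% at ρ = 0. The comparison of all 60 with all 59 stays near 5% throughout.

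**Step 6. Power.** With 59 controls and a true 10-point difference, power is Φ(10 / [20 × √(1/m + 1/59)] − 1.96): 78% for m = 60, 71% for m = 45 and 61% for m = 30.

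**The case against.** The case for the plan is substantial.

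- **The analysis is not primary.** Aim 1 is tested by ITT in a pilot trial. This stands, and it limits the consequence to the per-protocol result.
- **The stated grounds are exposure and adherence.** A reader might infer that the investigators intend to choose the cut-off by its effect on outcomes. The documents do not support that. Looking at an adherence distribution without outcomes is legitimate. What is missing is any safeguard that keeps the two apart.
- **Item 16c does not fix the cut-off.** A reader might see a fixed rule contradicted by item 15b, but item 16c itself calls the rule revisable. Item 15b also sits under how adherence will be presented and does not mention the per-protocol set. Linking the two is an inference, though a reasonable one, because both define who is adherent.
- **Adherers against all controls is not written down.** It is the natural reading, since controls cannot adhere, but the text is silent. The supportable statement is that the comparator and any adjustment are undefined.
- **The error rates rest on assumptions.** This stands. The fixed-rule figure depends heavily on how many are excluded: at ρ = 0.2 it is 11.5% with even adherence and 6.0% with adherence skewed high. The inflation from choosing among cut-offs persists in both, but only if someone chooses by p-value.

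**Conclusion.** The point holds for the per-protocol analysis. The plan states that its adherence rule may be set or changed at the analysis stage, when outcomes exist, without a lock or blinding. This is a written data-dependent rule, not merely a missing detail. The set is also open to selection bias, because membership depends on post-randomisation behaviour that only one arm can show.

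For 60 versus 59 with no true effect and ρ from 0 to 0.3, the false-positive rate is about 5% to 19% with a fixed 50% cut-off and even adherence, and about 5% to 6% if adherence is skewed high. It is about 12% to 39% if the most favourable of four cut-offs is picked. At ρ = 0 the excess is a multiplicity effect that falls about equally in either direction; at higher ρ it favours the intervention. These figures show direction and range and do not predict this trial's error rate.

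A reader might infer that the trial's main error rate is inflated. It is not: the primary ITT comparison does not use the adherence rule. The matter should be corrected but does not threaten the primary conclusion.

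**What to change.** 1. Use the rule already written in item 16c in both items. Delete the sentence in item 16c that allows revision and the one in item 15b that leaves the cut-offs to the analysis.
2. Lock the rule before adherence data are merged with outcomes. Label any other cut-off post hoc and report it beside the locked rule.
3. State that evaluable controls are the comparator. Adjust for baseline predictors of adherence, for example by inverse-probability weighting, and label the analysis supportive of ITT. Weighting removes only the selection that measured baseline variables explain.
4. A complier average effect is optional. It assumes no effect below the cut-off, yet someone receiving 40% of weeks still receives food. For illustration, let benefit rise linearly from 0 to 10 points with evenly spread adherence. The average effect is 5, half meet the rule, and the estimate is 5 / 0.5 = 10, while the true mean among those meeting it is 7.5. Random assignment is also not a clean instrument in an ITT set that requires a follow-up visit, when early withdrawals were 27 of 106 (25.5%) versus 4 of 86 (4.7%) (item 19). If this estimate is added, base it on everyone randomised where data allow, and state the assumption and its likely upward bias.

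The cost is SAP wording, a little extra analysis and a somewhat wider interval.
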